16 SAFETY ASSESSMENTS

16.1 Medical/Surgical/Medication History

The medical history (with demographic information, sialorrhea history with date of onset), should also include current co-morbidities, relevant past illnesses, all current medications (including those taken within 30 days before screening), surgical procedures performed within the prior 6 months, and past treatment(s) for sialorrhea.

As part of the screening medical history assessment and exclusion criteria review, subjects will be evaluated for presence or prior history of aspiration, aspiration pneumonia, choking, and/or dysphagia.

To ensure that these events are consistently rated across investigator sites, the definitions for the diagnosis and intensity provided in Section 16.2.4 should be used for

baseline evaluation and all subsequent assessments. The Investigator must determine, based on clinical evaluation, whether subsequent occurrences of aspiration, aspiration pneumonia, choking, and/or dysphagia during the study qualify as adverse events, as defined in Section 16.2.1.

16.2 Adverse Events

All adverse events and details for the events will be recorded on the subject's source document and on the Adverse Event eCRF. An adverse event should be documented in terms of a medical diagnosis. When this is not possible, the adverse event should be documented in terms of signs and/or symptoms observed or reported.

Adverse events can be collected by either the Investigator or the Study Coordinator; however, the Investigator must determine the intensity of the adverse event (Section 16.2.2.1), assess whether or not the study drug caused the adverse event (Section 16.2.2.2), record whether the adverse event led to discontinuation of the subject from the study (Section 16.2.2.3), record the outcome of the adverse event (Section 16.2.2.4), and determine if the adverse event is serious (Sections 16.2.2.5 and 16.2.6).

For this study, adverse events will be collected beginning with the start of dosing on Day 1 and will end at study completion (52 weeks \pm 1 week). Subjects who discontinue because of an adverse event before study completion will be contacted 13 weeks (\pm 3 days) after their last injection of study drug (see Section 16.2.7). Serious adverse events will be collected after signing informed consent until 30 days after study completion if the study site becomes aware of the event.

16.2.1 Definition of Adverse Event

An adverse event is defined as any untoward medical occurrence in a patient administered a medicinal product. An adverse event includes any noxious, pathologic, or unintended change in anatomic, physiologic, or metabolic functions as indicated by physical signs, symptoms and/or laboratory changes occurring in any phase of the clinical study whether associated with study drug, active comparator, or placebo, and whether or not considered to be drug related.

Examples include an exacerbation of pre-existing conditions or events, intercurrent illnesses, drug interaction, or the significant worsening of the disease under investigation that is not recorded elsewhere in the eCRF under specific effectiveness assessments. Anticipated fluctuations of pre-existing conditions that do not represent a clinically significant exacerbation or worsening need not be considered adverse events.

In clinical studies, an adverse event can include an undesirable medical condition occurring at any time during study participation, including run-in or wash-out periods, even if no study treatment has been administered.

Intercurrent illness and/or sequelae from intercurrent illness occurring between study screening/enrollment and dosing with study drug will be captured on the Adverse Event eCRF.

16.2.2 Investigator Assessment of Adverse Events

16.2.2.1 Intensity of Adverse Event

The Investigator must assess the intensity of each adverse event as mild, moderate, or severe as defined below.

- Mild: an awareness of symptoms but easily tolerated
- Moderate: symptoms interfering with daily activities
- Severe: incapacitating, with inability to perform normal daily activities

16.2.2.2 Relationship of Adverse Events to Study Drug

For each adverse event, the Investigator must assess the attribution of the study drug to the adverse event and determine whether the adverse event is or is not related to the study or test drug as defined below. The Investigator must also assess if the adverse event is related to the primary underlying condition/disease (e.g., PD, ALS). When in doubt, the adverse event should be considered at least “possibly related” to the study drug until further evidence becomes available to refute this assessment. Generally, an adverse event would not be considered related to both study drug and the underlying condition/disease.

Definitely Not Related

- Subject did not receive the test drug, the temporal sequence of the adverse event onset relative to administration of the test drug is not reasonable, or there is another obvious cause of the adverse event.

Possibly Related

- There is evidence of exposure to the test drug, the temporal sequence of the adverse event onset relative to administration of the test drug is reasonable, but the adverse event could have been due to another equally likely cause.

Probably Related

- There is evidence of exposure to the test drug, the temporal sequence of the adverse event onset relative to administration of the test drug is reasonable, and the adverse event is more likely explained by the test drug than by any other cause.

Definitely Related

- There is evidence of exposure to the test drug, the temporal sequence of the adverse event onset relative to administration of the test drug is reasonable, and the adverse event is more likely explained by the test drug than by any other cause, and the adverse event shows a pattern consistent with previous knowledge of the test drug or test drug class.

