Subjects whose risk of aspiration are judged by the investigator to be satisfactorily controlled by placement of PEG or G-tube for nutritional support are eligible to participate. Specific criteria excluding subjects with moderate to severe dysphagia or choking within the last 6 months prior to screening have been removed, and instead the protocol focuses solely on the risk of aspiration, taking into consideration that those with a PEG or G-tube (in whom placement of either would mitigate the risk of aspiration associated with a moderate to severe risk dysphagia or choking) may participate. The previous exclusion criteria could be considered too vague or restrictive as it focused on a symptom (dysphagia or difficulty with swallowing) that is common to many neurological disorders and especially frequent in ALS. The

revised inclusion/exclusion criteria now focus on the baseline risk of aspiration because it is aspiration that can lead to significant morbidity and even mortality.

- The requirement to administer the Visual Analog Scale (VAS) to subjects in order to rate severity for dysphagia and dry mouth at every clinic visit has been removed. Administering the scale at every visit, regardless of a reported event of dysphagia or dry mouth, is unnecessary and would result in an overreporting of events. Adverse events of dysphagia and dry mouth will continue to be collected based on subject report and severity will be determined by the Investigator.

Study drug injections should not be administered if an adverse event of dysphagia or dry mouth of moderate to severe severity persists without prior consultation with the Medical Monitor. If the adverse event has not resolved or has not improved to a mild severity by the end of the per protocol window for injections to occur (every 13 ± 2 weeks), the Medical Monitor should be contacted to discuss whether or not the subject should be dosed, discontinued, etc.

- Administrative updates have been incorporated, including a change in the Medical Monitor information.

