17.7 Statistical Methods for Safety

Frequency of treatment-emergent adverse events (TEAEs) will be calculated for each body system, by preferred term, and by treatment session, for number of subjects and proportion reporting the event and AESI. The incidence of subjects reporting TEAEs will also be reported without those TEAEs categorized as related to the primary underlying disease conditions by the Investigator. The severity of the adverse events and the relationship to study drug will be summarized for each body system and preferred term. Withdrawals due to adverse events will be summarized for each body system and preferred term. Narratives will be presented for all deaths, subjects reporting SAEs, and subjects withdrawn due to adverse events.

Vital signs and weight will be summarized descriptively for continuous variable at each pre-injection visit (i.e., Day 1, Weeks 13, 26, and 39) and at each post-injection time point of 4 weeks post-injection (i.e., Weeks 4, 17, 30, and 43), 8 weeks post-injection (i.e., Week 8, first Treatment Session only), and 13 weeks post-injection (i.e., Weeks 13, 26, 39, and 52). The change scores in weight, vital signs, and neurologic exam average score from pre-injection (i.e., Day 1, Weeks 13, 26, and 39) at 4 weeks post-injection (i.e., Weeks 4, 17, 30, and 43), 8 weeks post-injection (i.e., Week 8, first Treatment Session only), and 13 weeks post-injection (i.e., Weeks 13, 26, 39, and 52) will be analyzed, using a paired t-test where applicable, by treatment dose group defined in Section 17.3 for the safety population (i.e., low dose, medium dose, and high dose).

Neurologic exam average score will be summarized descriptively for continuous variable at baseline (Day 1, before first injection of study drug), and post-baseline Weeks 13 and 52. The change scores in neurologic exam average score from baseline at post-baseline time points will be analyzed, using a paired t-test where applicable, by treatment dose group

defined in Section 17.3 for the safety population (i.e., low dose, medium dose, and high dose).

Physical examination will be summarized for abnormal findings at pre-injection of each session and will be reported at post-injection Week 13 (i.e., Weeks 13, 26, 39, and 52), using shift tables.

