2.9.2 Safety analysis

Safety measures include adverse events, adverse events of special interest (AESI), dental adverse events (DAE), adverse events associated with distant spread of toxin effect, vital signs and weight, physical exam, neurological exam, dental exam, oral exam, and clinical laboratory tests, as well as lung functioning test for ALS subjects. Adverse events will be coded using the Medical Dictionary for Regulatory Activities (MedDRA) adverse event dictionary.

Like for effectiveness analyses, the baseline for safety analysis includes the pre-injection visits of Day 1, and Weeks 13, 26, and 39, respectively, for each of the treatment sessions 1 through 4.

Drug Exposure

Frequency of drug exposure will be calculated based on the number of injections of study drug administered. Duration of drug exposure will be calculated for each subject for the average duration of individual treatment sessions and total duration of treatment sessions, with the former being the average of the durations of individual treatment sessions the subject has received and the latter being the sum of the durations of individual treatment sessions the subject has received. Duration of drug exposure will be summarized for the safety population as defined in Section 3.1.

Early Termination

Subjects' study disposition will be summarized. A listing will be provided for all early terminations. This listing will include a subject's demographic variables, primary diagnosis, number of injections administered, and the primary reason for early termination.

Adverse Events, AESI, and DAE

All of adverse events will be coded for preferred terminologies using MedDRA. An AE that occurs on the 1st injection date or later will be defined as a TEAE. An AE with start date missing and no valid stop date or stop date being after the first injection date will be considered as a TEAE. TEAEs will be further separated by treatment session.

TEAEs, AESIs, DAEs, and adverse events associated with distant spread of toxin effect will be analyzed by session. Frequency of these types of adverse events will be calculated for each body system (or system organ class, SOC), by preferred term, for number of subjects and proportion reporting the event. The severity of adverse events and the relationship to study medication will be summarized for each body system and preferred term.

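### The causality section discourages attributing an adverse event to both drug and disease, and the protocol's reduced TEAE summary drops every disease-attributed event whatever its drug rating

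*Protocol*

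**What the plan says.** Protocol 16.2.2.2 requires a rating of each event against study drug on four levels: Definitely Not, Possibly, Probably and Definitely Related. It then requires a second rating: "The Investigator must also assess if the adverse event is related to the primary underlying condition/disease (e.g., PD, ALS"). Three further pieces of the section matter here.

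- A lean towards the drug, at the Possibly Related level, under uncertainty: "When in doubt, the adverse event should be considered at least" possibly related.
- Immediately afterwards, a default against dual attribution: "Generally, an adverse event would not be considered related to both study drug and the underlying condition/disease".
- The level definitions. Possibly Related needs exposure and reasonable timing, "but the adverse event could have been due to another equally likely cause". Definitely Not Related can be met on one ground alone: "or there is another obvious cause of the adverse event".

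Protocol 17.7 tabulates all TEAEs and adds a second incidence, "reported without those TEAEs categorized as related to the primary underlying disease conditions by the Investigator". No condition on the drug rating is attached.

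SAP 2.9.2 says: "The severity of adverse events and the relationship to study medication will be summarized for each body system and preferred term". SAP 5.3 repeats this by treatment session. Neither section describes the reduced summary or any use of the disease rating.

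**The concern.** The primary objective is long-term safety and tolerability, and there is one arm. No control rate would reveal events credited to the wrong cause, so the investigator's ratings matter more than they would in a randomised trial.

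The events most exposed are those the protocol singles out: aspiration, aspiration pneumonia, choking and dysphagia. Its amendment summary describes dysphagia as "common to many neurological disorders and especially frequent in ALS". A drug effect on swallowing may therefore appear as a worsening of something the disease already causes. For such an event the accurate record is that both contributed, and that is the record the default discourages. At stake is whether the drug-relationship table and the reduced TEAE summary can be read at face value for these events.

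**Working it through.** There is no figure in the plan to reproduce, and the documents give no event rate and no share of events attributed to disease. The check is a cross-reading of the rules.

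**Step 1: possible records.** Four drug levels times two disease answers gives 4 × 2 = 8 combinations per event.

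| Disease-related | Drug rating | Combinations | Reduced summary, 17.7 as written | Rule proposed here |
|---|---|---|---|---|
| No | Any level | 4 | Kept | Kept |
| Yes | Definitely Not | 1 | Dropped | Dropped |
| Yes | Possibly, Probably or Definitely | 3 | Dropped | Kept |

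As written, 17.7 drops 1 + 3 = 4 combinations. The 3 in the last row carry a positive drug attribution and are dropped all the same. They are also exactly the combinations that the default sentence discourages.

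**Step 2: follow an event with mixed causes through the rules.**

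- *The investigator is in doubt.* The drug rating becomes at least Possibly Related. If the default is then applied, the disease rating is No. The event stays in the drug-related counts and in the reduced summary. What is lost is the disease contribution, so the error runs against the drug.
- *The investigator favours disease but suspects aggravation by the drug.* If the default is applied, disease is Yes and the drug should not be rated as related. The scale has no unlikely level, so the only rating left is Definitely Not Related, which the obvious-cause ground can support. The event sits in the not-related row of the drug-relationship table and leaves the reduced summary.
- *The investigator rates both.* The drug-relationship table is right, but the reduced summary drops the event.

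**Step 3: why both places need changing.** If the default is followed without exception, the last row of the table is empty and the 17.7 rule does no added harm; the information has been lost at rating. If only the default sentence is removed, more events may be rated as both, and 17.7 as written would drop them. Correcting one place without the other leaves the problem.

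**Step 4: which tables are touched.**

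| Planned output | Depends on a causality rating? |
|---|---|
| All TEAEs by session (Protocol 17.7; SAP 2.9.2, 5.3) | No |
| Events of special interest (SAP 5.4) | No |
| Distant spread of toxin effect, from a term list that includes aspiration, dysphagia and aspiration pneumonia (SAP 5.6) | No |
| Relationship to study drug (Protocol 17.7; SAP 2.9.2, 5.3) | Yes, drug rating |
| Reduced TEAE incidence (Protocol 17.7 only) | Yes, disease rating |

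**The case against.** The case for leaving the text alone is substantial.

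- *The default is hedged.* It says what generally applies and forbids nothing; two ratings are still required. This stands, so the conflict is a tension in the instructions and not a prohibition. But no guidance says when an exception is proper, so sites may differ.
- *The tie-break protects ambiguous events.* This stands for an investigator who feels doubt. It does not help when the investigator is confident that disease is the main cause but the drug may have added to it. Removing the default sentence would also leave the obvious-cause ground in place.
- *No event disappears.* The unfiltered tables keep all of them, and events of special interest go to the sponsor within 24 hours whatever the cause (Protocol 16.2.8.1). This stands, with one limit: the dysphagia criteria in Protocol 16.2.4.3 call for new onset, so worsening of existing dysphagia may not clearly count as an event of special interest. It could still be recorded as an adverse event, since Protocol 16.2.1 includes exacerbation of existing conditions.
- *The affected summary is supplementary, and the SAP does not describe it.* Both are true. The second is itself a gap between protocol and SAP. The list of table shells was not in the text available for this review, so nothing can be said about whether the table was planned there.

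A reader might infer that the rule biases the drug-related rate of special-interest events downward. The documents do not support this: SAP 5.4 describes no drug-related rate for those events, and the tie-break pushes doubtful cases the other way.

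**Conclusion.** The inconsistency is real and should be fixed, but it does not undermine the safety evaluation as a whole. Protocol 16.2.2.2 offers a drug-related category built for shared plausibility and then discourages recording shared causation. Information is lost in two situations: when an investigator who favours disease leaves drug aggravation unrecorded, and when an event rated as both is removed by 17.7 despite its drug attribution.

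The effect is confined to the drug-relationship tabulation and the 17.7 reduced summary. Its size cannot be derived from the documents, and any percentage would rest on invented event counts. For events in genuine doubt even the direction is open. For the two situations named, the direction is clear: the drug-related count, the reduced incidence, or both can only be lower than under independent ratings.

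This rests on two assumptions: that investigators give the default sentence some weight, and that the reduced summary is produced as Protocol 17.7 describes.

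**What to change.** 1. **Protocol 16.2.2.2:** delete the sentence against dual attribution, or reword it to say that an event may be related to both. Record the two ratings as independent items on the adverse event eCRF, with completion guidance that a disease rating does not settle the drug rating.
2. **Protocol 17.7:** exclude from the reduced summary only events rated disease-related AND Definitely Not Related to study drug. Make this change together with item 1.
3. **SAP 2.9.2 and 5.3:** state whether the reduced summary is produced and, if so, under this rule.
4. **If data collection is complete:** SAP 3.4 already reports that the safety and ITT populations differ by one subject, so the ratings may no longer be open to change. The exclusion rule can still be applied, and events of special interest can be cross-tabulated by drug rating and disease rating. That table would show how many events were rated as both. It cannot recover drug aggravation that was never recorded.

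The cost is an edit to one sentence, eCRF guidance, a changed exclusion condition, a statement in the SAP and one cross-tabulation. The downside is that the reported rates may be slightly less favourable to the drug.

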16.2.2.3 Action Taken with Regard to Study Continuation/Discontinuation

For each adverse event, the Investigator must indicate whether or not the adverse event caused the subject to discontinue from the study (more than one adverse event may be associated with the decision to discontinue a subject).

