7 BACKGROUND AND SIGNIFICANCE

8 STUDY OBJECTIVES

8.1 Primary Objective

The primary objective of this study is:

- To determine the long-term safety and tolerability of MYOBLOC (administered intraglandularly as a single total dose of 3,500 Units) treatments every 13 weeks over a maximum possible duration of 1 year in adult subjects with troublesome sialorrhea.

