13.2 Study Drug Administration and Compliance

Subjects will receive single dose injections of MYOBLOC every 13 weeks (± 2 weeks) for a maximum total of 4 treatments. MYOBLOC will be injected first into the submandibular glands (right and then left) followed by the parotid glands (right and then left)

- Total dose of 3,500 Units (0.7 mL) of MYOBLOC with 1,500 Units (0.3 mL) injected into each parotid gland and 250 Units (0.05 mL) injected into each submandibular gland.

Subsequent injections at each treatment session will be done when subjects return to baseline status as determined by the Investigator, with a minimum interval of 11 weeks from the prior injection. Study drug injections should not be administered if an adverse event of dysphagia or dry mouth of moderate to severe severity persists without prior consultation with the Medical Monitor. If the adverse event has not resolved or has not improved to a mild severity by the end of the per protocol window for injections to occur (every 13 ± 2 weeks), the Medical Monitor should be contacted to discuss whether or not the subject should be dosed, discontinued, etc.

If after the first treatment of 3,500 Units the subject develops intolerable side effects, but still wishes to remain in the study, the Investigator has the discretion to decrease subsequent doses, but to no less than a total dose of 2,500 Units. If this does occur, the total dose can therefore be 2,500 Units to 3,500 Units of MYOBLOC. The Investigator must clearly indicate the adjusted dose given. MYOBLOC will be injected first into the submandibular glands (right then left) followed by the parotid glands (right then left) as follows:

- Total dose of 2,500 to 3,500 Units (0.5 mL to 0.7 mL) of MYOBLOC with 1,000 to 1,500 Units (0.2 mL to 0.3 mL) injected equally into each parotid gland and 250 Units (0.05 mL) injected into each submandibular gland.

All MYOBLOC injections will be performed by Investigators who have prior experience or have been appropriately trained with injecting botulinum toxin and such experience/training will be documented in the study records. Injections will be guided by external anatomical landmarks or by external anatomical landmarks with ultrasound-guided confirmation (Appendix A). Sites designated as “ultrasound” sites will perform all their injections with ultrasound-guidance.

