4.2 Treatment Compliance

For this study, the overall compliance rate will be summarized by demographic parameters for the safety population. For a treatment session, the compliance rate, expressed as percent, is calculated by dividing the number of drug injections into the 4 locations of the submandibular and parotid glands by the total number of 4 injections that should have been given during a treatment session multiplied by 100. For a subject, the overall compliance rate is defined as the average of compliance rates for all treatment sessions.

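### No described record or SAP table links a reduced or held dose to the adverse event behind it, and the compliance formula gives 100% for a 2,500-Unit session, so intolerance of 3,500 Units short of withdrawal is not counted.

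*Protocol*

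**What the plan says.** Protocol 8.1 sets the primary objective: "To determine the long-term safety and tolerability of MYOBLOC (administered intraglandularly as a single total dose of 3,500 Units"), given every 13 weeks for up to a year. The safety endpoints in Protocol 9.1 are adverse events, events of special interest, C-SSRS and dental events. None is a separate tolerability measure.

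Protocol 13.2 describes two responses to poor tolerance that fall short of withdrawal:

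- **Lower dose.** If the first 3,500-Unit treatment causes intolerable side effects and the subject wishes to stay, "the Investigator has the discretion to decrease subsequent doses, but to no less than a total dose of 2,500 Units". The adjusted dose must be recorded.
- **Held injection.** "Study drug injections should not be administered if an adverse event of dysphagia or dry mouth of moderate to severe severity persists", unless the Medical Monitor has been consulted first.

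On action taken, Protocol 16.2.2.3 has one item: "the Investigator must indicate whether or not the adverse event caused the subject to discontinue from the study". Protocol 16.2 repeats it among the Investigator's duties: "record whether the adverse event led to discontinuation of the subject from the study".

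The SAP (2.9.2 and 5.3) summarises withdrawals and early terminations due to adverse events. SAP 2.9 puts every statistical table under a single any-dose group and keeps dose categories for listings. SAP 4.2 computes session compliance by "dividing the number of drug injections into the 4 locations of the submandibular and parotid glands by the total number of 4 injections", times 100. For a subject, "the overall compliance rate is defined as the average of compliance rates for all treatment sessions".

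**The concern.** A subject who cannot tolerate 3,500 Units and continues on a lower dose has met the protocol's own condition for intolerance. Under the plan as described, that subject appears as fully compliant, sits in the pooled dose group, and has no event marked as having changed treatment. The same applies to a subject whose injection was held for an adverse event and who stayed in the study.

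The only treatment-limiting outcome that is tabulated is withdrawal. If reductions and holds are more than a handful, the withdrawal figure alone gives an incomplete answer on tolerability of the dose named in the primary objective. The dose distinction matters elsewhere in the plan too: Protocol 11.1 separates exposure at 2,500 Units or more from exposure at 3,500 Units when it sets the safety database targets.

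**Working it through.** **1. Reproduce the protocol's dose figures.** Inputs are from Protocol 13.1 and 13.2: 5,000 Units per mL, two parotid and two submandibular glands.

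- Full dose: 2 × 1,500 + 2 × 250 = 3,500 Units; 3,500/5,000 = 0.7 mL.
- Lowest permitted dose: 2 × 1,000 + 2 × 250 = 2,500 Units; 2,500/5,000 = 0.5 mL.

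Both match the protocol, and both use four injections. Only the amount per parotid gland differs.

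**2. Apply SAP 4.2.** Session rate = (sites injected / 4) × 100; subject rate = mean of the session rates. Compare with dose intensity = Units given / 3,500 per session.

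| Subject | SAP 4.2 | Units given / 3,500 per session |
|---|---|---|
| Four sessions at 3,500 | 100% | 14,000/14,000 = 100% |
| One session at 2,500 | 4/4 = 100% | 2,500/3,500 = 71.4% |
| 3,500, then three at 2,500 | 100% | 11,000/14,000 = 78.6% |
| Four sessions, one gland missed once | (100 + 100 + 100 + 75)/4 = 93.75% | not applicable |

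Units do not enter the formula. Among sessions given, only a missed gland lowers the rate.

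**3. The session denominator.** SAP 4.2 does not say which sessions are averaged. SAP 2.9.1 defines a session as an injection plus its follow-up, so sessions received is the natural reading. For a subject who stops after one fully injected session, the rate is 100% over sessions received, 50% over the two required sessions and 25% over the four possible ones. The 2,500-Unit result in step 2 does not depend on this choice.

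**4. Look for a link between dose change and event in the other outputs.**

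- SAP 3.2 summarises by session the subjects who received doses, and SAP 3.6 lists dose, date and time. Neither gives a reason.
- SAP 5.1 tabulates the number of injections (1 to 4) and session durations, not Units.
- SAP 5.3 tabulates all treatment-emergent events by incidence, severity and relationship. SAP 5.4 covers dysphagia, and SAP 5.6 includes dry mouth. None shows whether the event changed the next dose.
- SAP 2.9.2 and 5.3 link events to treatment only through withdrawal or termination.

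**5. What the missing count could look like.** The documents give no rate, so the counts here are assumptions. SAP 2.5 gives 187 subjects; taking all as treated, exact 95% intervals are:

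- 0/187: 0 to 2.0%
- 9/187 (4.8%): 2.2 to 8.9%
- 19/187 (10.2%): 6.2 to 15.4%
- 37/187 (19.8%): 14.3 to 26.2%

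Even a count of zero would be informative, since it would bound the rate at about 2%.

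**The case against.** The strongest reply is that the data exist and only a table is missing. The protocol allows a lower dose for one reason, intolerable side effects, and SAP 2.2 likewise ties it to poor tolerability. If sites follow the protocol, any recorded dose below 3,500 Units already marks intolerance. Dose and date are listed, and every treatment-emergent event is listed by subject. The eCRF and the table shells are not among the documents, so a reason field or a suitable table may exist. Most of this stands. It does not identify which event led to the reduction, it does not separate an injection held for an event from one timed for other reasons, and the plan as described does not commit to the count.

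It can also be said that SAP 4.2 measures whether the four glands were injected, and that a permitted reduction is not non-compliance. That is fair. It is a reason to add a dose measure beside the site count, not to replace the site count.

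Three stronger readings might be inferred, and the documents do not support them:

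- **That a subject stopped for an adverse event after one session is hidden.** Only the compliance rate can hide this, and only on one reading of its denominator. The subject appears in disposition (SAP 3.6), the termination listing with number of injections and reason (SAP 2.9.2), the injection counts (SAP 5.1), the adverse-event termination summary (SAP 5.3) and a narrative.
- **That every late injection is intolerance.** Protocol 10 times each injection to the subject's return to baseline, between 11 and 15 weeks after the last. A delay within that window may simply mean a longer effect.
- **That the reported tolerability rate is wrong by some stated factor.** No reduction or hold rate is given. SAP 2.9 says only that the majority received 3,500 Units.

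**Conclusion.** The point holds in a limited form. Intolerance of 3,500 Units that led to a lower or held dose, but not to withdrawal, is not counted in any described record or table. The compliance rate cannot reveal a reduction: it gives 100% for a session at 71.4% of the named dose, and 100% for a course at 78.6% of it. The adverse events themselves, the doses and dates, and the withdrawals are all reported.

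The number of subjects affected is unknown and may be small. The 78.6% figure assumes four sessions with all three later doses at the lowest permitted level; the 71.4% figure needs no assumption about the number of sessions. The conclusion about records rests on the protocol and SAP text, since the eCRF was not available. This is a gap in reporting against the primary objective that is worth closing; it does not make the safety data unusable.

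**What to change.** 1. **Record the link.** Extend the action-taken item in Protocol 16.2.2.3 and the adverse-event eCRF to cover dose reduced, and injection delayed or withheld, because of the event. The SAP (dated July 2018) already describes some results in the past tense, so collection may be over. In that case, derive the link by matching dose and date records to adverse events, and state the matching rule.
2. **Add one table.** In SAP 2.9.2 and 5.3, tabulate over the whole study, by preferred term, the subjects with an adverse event leading to dose reduction, to delay or withholding for that event, or to withdrawal. Leave out delays made only because the subject had not returned to baseline.
3. **Add a dose measure.** In SAP 4.2 or 5.1, report Units given / 3,500 per session received as dose intensity, alongside the site-count compliance. State which sessions the overall rate averages.
4. **Reconcile the dose categories used in listings.** Protocol 17.3 puts 2,500 Units in the low group (2,500 to 2,999). SAP 2.9 puts it in the medium group (2,500 to 3,000), sets its low group at 1,500 to 2,000, and has no category for 3,001 to 3,499.

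No dosing rule changes. The cost is a short code list or a matching step, one table and one ratio. The downside is a tolerability figure that may look slightly less favourable.
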